5.2 Treatment Dosage and Administration

Subjects in this trial will be administered entinostat, 5mg PO, once weekly (D1, D8, D15 of a 21-day cycle) starting on day 1 of study treatment. Pembrolizumab, 200 mg will be administered intravenously (IV) every 3 weeks and initiated at cycle 2 after the mandatory research tumor biopsy in the end of cycle 1, beginning of cycle 2 (day 22±2 days). Combination therapy with both agents will continue if subject is receiving clinical benefit from therapy for up to 27 weeks (8 cycles of combination therapy or approximately 6 months). Study therapy will be discontinued for intolerable toxicity, disease progression or for other reasons at the discretion of the investigator.

Agent	Required Premedications; Precautions	Dose	Route	Schedule	Cycle Length
Entinostat	Take on an empty stomach i.e., at least 2 hours after a meal and at least 1 hour before the next meal.	5 mg ³	Oral (PO)	Start on study D1 of cycle 1 and administer once weekly (i.e., D1, D8, D15 of each cycle) for 9 cycles qwk) (±1 day)	Every 21* days
Pembrolizumab	Risk for immune-mediated ¹ and infusion-related ² reactions	200 mg ³	IV; administer over 30 min (range -5, +10 min)	Start on study D22 (± 2 days) of the study (i.e., D1 of cycle 2) and administer every 21 (± 2) days (q3wk) x 8 cycles (i.e., cycles 2-9)	

1. See Section 5.3.2 for management guidelines for immune-mediated AEs.
2. See Section 5.6.1 for management guidelines for infusion-related AEs
3. On days when entinostat is administered on the same day as pembrolizumab, entinostat should be taken before the pembrolizumab infusion.

*Entinostat monotherapy for cycle 1 and combination therapy should be initiated on D1 of cycle 2 and continue until withdrawal for toxicity, withdrawal for patient preference, disease progression or the subject completes 27 weeks of protocol-directed therapy. Entinostat cannot be continued beyond the 27-week duration of study-directed therapy for the trial, irrespective of treatment response.

*Pembrolizumab will be started on D22 of the study (i.e., D1 of cycle 2) and may continue for up to 24 weeks in combination with entinostat (i.e. cycles 2-9). Following completion of the trial therapy at 27 weeks and on condition that there is no disease progression, pembrolizumab can be continued per investigator discretion, as per standard of care guidelines.

5.2.1 Drug Dosing Schema

Cycle length (21 days)	Cycle 1			Cycle 2			Cycle 3			Cycle 4			Cycle 5		
Study Day Week	D1 Wk 1	D8	D15	D22 WK 4	D29	D36	D43 Wk 7	D50	D57	D64 Wk10	D71	D78	D85 Wk 13	D92	D99 Wk 15
Entinostat PO, once weekly	X	X	X	X	X	X	X	X	X	X	X	X	X	X	X
Pembrolizumab IV, q3W				X			X			X			X		

Cycle length (21 days)	Cycle 6			Cycle 7			Cycle 8			Cycle 9		
Study Day Week	D106 Wk 16	D113	D120	D127 WK 19	D134	D141	D148 Wk 22	D155	D162	D169 Wk25	D176	D183 Wk27
Entinostat PO, once weekly	X	X	X	X	X	X	X	X	X	X	X	X
Pembrolizumab IV, q3W	X			X			X			X		

Figure 1. Study medications should be administered during the weeks denoted above. See the schedule of assessments in Section 7.1 for further details. On days when entinostat is administered on the same day with pembrolizumab, entinostat should be administered before the infusion of pembrolizumab.

5.3 Toxicities and Dosing Delays/Dose Modifications

Any subject who receives at least one dose of entinostat on this protocol will be evaluable for toxicity. Each patient will be assessed periodically for development of any toxicity according to the Time and Events table in section 7.1. Toxicity will be assessed according to the NCI-CTCAE v5.0. No dosing adjustments will be made for pembrolizumab, but delays in dosing or discontinuation of pembrolizumab and entinostat may be required. Depending on the side effects related to pembrolizumab administration, there would be either treatment delays (i.e., delays up to 3 days of scheduled dose if AE(s) occur prior to cycle 3 or 4, up to 7 days of scheduled dose allowed if AE(s) occurs prior to cycles 5 and 6; delays up to 15 days of scheduled dose allowed for pembrolizumab infusions if AE(s) occurs for cycle 7, 8 or 9 of combination treatment). If pembrolizumab delays go beyond what is allowed, subject will skip the particular dose and a note will be made regarding the reason. If pembrolizumab is permanently discontinued, then entinostat must also be discontinued. Entinostat dosing guidelines and delays are provided in the section below.

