2.2 Secondary Objectives

- 2.2.1 Assess antitumor response rate to the pembrolizumab-entinostat combination in patients with ‘non-inflamed’ melanomas (TIL/TAL-absent by histopathologic analysis of H&E-stained tissue section from archived metastatic melanoma tumors) irrespective of prior PD-1/PD-L1 inhibitor treatment status after 3 cycles (9 weeks) of study treatment by RECIST v1.1 criteria.
- 2.2.2 Assess the 6-month (i.e. 27 weeks) progression-free survival (PFS) rate in patients with ‘non-inflamed’ (TIL/TAL-absent), irrespective of prior PD-1/PD-L1 inhibitor treatment status treated with the pembrolizumab-entinostat combination by RECIST v1.1 criteria.
- 2.2.3 Assess toxicity of the concurrent pembrolizumab-entinostat combination based on NCI-CTCAE v.5.0.

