3.2 Secondary Endpoints

- 3.2.1 The ORR (CR + PR) at 10 weeks will assessed based on RECIST v1.1 criteria.
- 3.2.2 PFS rate at approximately 6 months (i.e. 27 weeks) is defined as the time from day 1 of treatment until disease progression or death status measured 6 months after initiating study treatment. Progression events will be defined per RECIST v1.1 criteria.
- 3.2.3 The toxicity will be assessed based on the NCI CTCAE v 5.0 criteria. For example, the incidence of AEs that occur in subjects enroll who receive at least one dose of therapy.

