6.1.4 Entinostat Compliance

Treatment compliance for entinostat dosing will be assessed at the end of each cycle, defined as 3 weeks (21 days). The first cycle on study will consist only of entinostat (mono-therapy). All 21-day cycles of treatment on study thereafter will include entinostat in combination with pembrolizumab. Patients will complete the IRB-approved dosing diary for documenting date and time of each weekly entinostat dose. Subjects will be instructed to bring all study IP (including partially used bottles) to each visit, including their subject dosing diary. The dates of any missed doses will also be recorded in the subject dosing diary. Site staff will perform accountability of the returned drug. Patient compliance will be assessed.

Site staff must ensure that the patient clearly understands the directions for self-administration of study drug and complies with the schedule provided.

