7.7 Assessment of Safety

Any patient who receives at least one dose of entinostat will be evaluable for toxicity. Each patient will be assessed periodically for the development of any toxicity according to the Time and Events table. Toxicity will be assessed according to the NCI CTCAEv5.0.

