8.2 Documentation of non-serious AEs or SARs

For non-serious AEs or SARs, documentation must begin from day 1 of study treatment and continue until patient completes the 30-day follow-up period assessments.

Collected information should be recorded in the eCRF and source documentation appropriately. Please include a description of the event, its severity or toxicity grade, onset and resolved dates (if applicable), and the relationship to the study drug. Documentation should occur at least monthly.

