9.1.1 Definitions

Evaluable patients are those who complete all activities by at least day 22, namely: (a) they have received at least one and up to 4 entinostat weekly doses on day 1 and day 8, 15 and 22 (b) they have received the first pembrolizumab infusion on day 22 (± 2 days), and (c) they have completed day 22 (± 2 days) mandatory tumor biopsy. The rationale for this is to answer the primary translational endpoint regarding entinostat-alone immunomodulatory effects in peripheral blood and tumor tissue with sufficient power.

- SAE are events that meet FDA's definition as defined in [section 8.1.4](#) of the protocol irrespective of attribution to study drug(s). Subjects who receive at least one dose of entinostat are evaluable for safety.

- ORR by RECIST 1.1 criteria is the sum of complete response and partial response.

- PFS is measured from the date of enrollment on study to the date of documented progression. The rate of patients who are progression-free will be specifically calculated at 27-weeks (approximately 6 months) from study entry.

- OS is measured from the date of enrollment on study to the recorded date of death. The rate of patients who are alive at 27-week (approximately 6 months) will be specifically calculated for the study.

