9.3 Data Analysis Plans

Tumor response and AE of the entinostat-pembrolizumab combination will be tabulated and 95% confidence interval will be computed. PFS and OS will be estimated using Kaplan Meier method.

[REDACTED] The tumor imaging at baseline and on day 22, the peripheral blood assessment, and the baseline assessments for targeted mutation panel sequencing (FoundationOne®, or other targeted panel sequencing commercially available panel) are secondary correlative endpoints.

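### The safety objective concerns the concurrent combination, but the only defined safety set is everyone given one entinostat dose, with no split at the first pembrolizumab infusion

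*Combined protocol and SAP*

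**What the plan says.** Secondary objective 2.2.3 reads: "Assess toxicity of the concurrent pembrolizumab-entinostat combination based on NCI-CTCAE v.5.0". Section 9.3 carries it into the analysis: "Tumor response and AE of the entinostat-pembrolizumab combination will be tabulated and 95% confidence interval will be computed". That sentence names neither the patients nor the period over which AEs are counted.

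The set of patients assessed for safety is given in several places:

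- Section 5.3: "Any subject who receives at least one dose of entinostat on this protocol will be evaluable for toxicity".
- Section 7.7: "Any patient who receives at least one dose of entinostat will be evaluable for toxicity".
- Section 9.1.1: "Subjects who receive at least one dose of entinostat are evaluable for safety".
- Section 3.2.3, as an example of the toxicity endpoint: "the incidence of AEs that occur in subjects enroll who receive at least one dose of therapy". No drug is specified.

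Sections 5.2 and 6.1.4 make cycle 1 entinostat monotherapy, with pembrolizumab starting on day 22 (±2 days). For non-serious AEs, section 8.2 says "documentation must begin from day 1 of study treatment and continue until patient completes the 30-day follow-up period assessments"; section 8.3.1 likewise starts the recording of serious events on day 1. Section 6.3.5 records start and stop dates, grade and relation to study drug.

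Section 9.1.1 also defines evaluable patients, who must have had the first pembrolizumab infusion and the day 22 biopsy. That definition serves the primary endpoint and is not applied to safety.

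**The concern.** The objective describes patients receiving both drugs at once. The safety set describes anyone who started the run-in. The two differ in two ways.

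- **Denominator.** A patient who stops during cycle 1 cannot have an AE on the combination, yet is counted. This lowers the rate.
- **Numerator.** A patient whose only event falls in cycle 1 counts as a case, although pembrolizumab had not been given. This raises the rate.

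Both routes are plausible. Section 9.2 expects some patients to be lost to toxicity or rapid progression. Section 1.4.6.2.2 reports single-agent entinostat events in solid tumours graded as serious, such as fatigue (13%) and dyspnea (9%). At stake is whether the figure reported for objective 2.2.3 describes the exposure that the objective names. Because the net error can take either sign, a reader cannot correct for it from the pooled table.

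**Working it through.** **1. The plan's own figures.** The documents state no toxicity rate and no sample size for safety. The nearest figures are the exact 95% intervals for response in section 9.2. The Clopper-Pearson limits for x cases in n patients are:

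- lower = 2.5% quantile of Beta(x, n − x + 1)
- upper = 97.5% quantile of Beta(x + 1, n − x)

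For 0/10 this gives (0, 0.308); the plan states (0, 0.31). For 1/10 it gives (0.003, 0.445); the plan states (0, 0.45). The figures are reproduced, and the same method is used below.

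**2. Inputs.**

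- Patients dosed: 14. This is the enrolment target in section 9.2, assumed here to be all dosed.
- Patients dosed but never given pembrolizumab, m: assumed 0 to 3. The top value is the full 20% loss in section 9.2 (0.20 × 14 = 2.8). That 20% includes screen failures, who never receive entinostat and so enter neither denominator. Three is therefore an upper-end value.
- Patients with an event in the combination period: assumed 3.
- Other patients with an event in cycle 1 only, y: assumed 0 to 2.

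**3. Denominator effect (y = 0).** The pooled rate is 3/14 = 21% (5-51%) throughout. The rate among patients given pembrolizumab is 3/(14 − m):

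| m | Rate among exposed | 95% CI |
|---|---|---|
| 0 | 3/14 = 21% | 5-51% |
| 1 | 3/13 = 23% | 5-54% |
| 2 | 3/12 = 25% | 5-57% |
| 3 | 3/11 = 27% | 6-61% |

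At m = 3 the pooled rate is 27.3 − 21.4 = 5.9 points too low.

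**4. Numerator effect added (m = 3).** The pooled rate is (3 + y)/14; the combination-period rate stays at 3/11 = 27% (6-61%).

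| y | Pooled rate | 95% CI | Pooled minus 27.3% |
|---|---|---|---|
| 0 | 3/14 = 21.4% | 5-51% | −5.9 points |
| 1 | 4/14 = 28.6% | 8-58% | +1.3 points |
| 2 | 5/14 = 35.7% | 13-65% | +8.4 points |

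The sign changes between y = 0 and y = 1. The intervals for 3/14, 3/11 and 5/14 are about 46, 55 and 52 points wide, so every shift shown is small beside the sampling uncertainty.

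**The case against.** The strongest reply is that section 9.3 names no AE denominator. Sections 5.3, 7.7 and 9.1.1 say who can be assessed for safety, not who forms the denominator of a combination rate. Read literally, 9.3 might already mean events after pembrolizumab starts, and some of its text is redacted. This stands in part: use of the entinostat-dosed set is inferred, because no other safety set is defined. The visible text after the redaction concerns correlative endpoints. If 9.3 does intend combination-period events, the plan still gives no matching set or period.

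Second, the protocol uses combination loosely. Section 5.1 speaks of 27 weeks of combination therapy, which includes cycle 1, and all-treated safety is sound for the regimen as a whole. That justifies keeping the overall table. It does not make that table an answer to an objective worded as concurrent treatment, and section 5.2 itself counts 8 combination cycles.

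Third, relation to study drug is recorded, so attribution might do the work. But section 5.3.2 concedes that attribution to one drug is likely to be difficult, and section 5.3.3 lists overlapping toxicities. Onset date is a firmer divider, although it does not establish cause either: section 1.4.6.2.1 gives entinostat a mean terminal half-life of about 194 hours (194/24 ≈ 8 days), and entinostat dosing continues alongside pembrolizumab.

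A reader might also infer that sequential dosing was chosen to separate the two toxicity profiles. Section 9.1 gives a different reason: correlative study of immunomodulatory effects. No listed objective asks for entinostat-alone toxicity.

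**Conclusion.** The mismatch between objective and safety set is real and worth correcting. Followed as written, the plan would give objective 2.2.3 a rate that mixes cycle 1 monotherapy events and patients never given pembrolizumab with combination exposure. This rests on the inference that 9.3 uses the only safety set defined.

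The size is modest. With the assumed counts, the pooled rate runs from 5.9 points below to 8.4 points above the combination-period rate, inside intervals some 50 points wide. The counts are illustrative and m = 3 is upper-end.

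Two stronger readings are not supported. One is that the planned rate must understate combination toxicity; the direction depends on how many cycle-1-only cases occur. The other is that a trial conclusion would change; this is a descriptive secondary endpoint in an exploratory study, and the readable text ties no threshold or stopping rule to it.

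**What to change.** In section 9.3, keep the overall AE table in all patients given at least one entinostat dose, and add tables for two periods:

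1. Onset before the first pembrolizumab infusion. Denominator: at least one entinostat dose.
2. Onset, or worsening in grade, from the first pembrolizumab infusion onward. Denominator: at least one pembrolizumab infusion.

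Use the second for objective 2.2.3, with its 95% interval, and describe it as AEs during the combination period, not as AEs caused by the combination. Count patients, not events. State how events dated on the day of the first infusion are placed, since the biopsy may fall on the same day.

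This is a free improvement: the extra tables use dates and grades already recorded under section 6.3.5, with no new visits, samples or patients. One practical check is needed. The documents do not say whether a change in grade is entered with its own date, and the worsening rule needs that.

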5.3.1 Entinostat Dosing Modification Guidelines

All dose modifications should be based on the AEs requiring the greatest modification and also meet criteria for dose adjustment. AEs should be properly documented in source documents. Investigators may take a more conservative approach than the guidelines outlined below based on clinical judgment that is in the best interest of the subject.

Management of toxicities that are at least possibly related to entinostat, with toxicities graded by the Investigator according to the NCI, CTCAE, version 5.0 should be managed as follows:

Non-hematologic Toxicity	
Toxicity	Dose Modifications for Entinostat
Grade 4	Administer symptomatic remedies/start prophylaxis. Hold dose until recovery to Grade 1 or baseline under the following directions: 
 1. If recovered within 4 weeks of onset (i.e.: ≤ 3 missed doses), resume study drug as follows: 
 • If receiving 5 mg, restart study drug at 3 mg, • If receiving 3 mg, restart study drug at 2 mg, • If receiving 2 mg, discontinue study treatment. 2. If not recovered within 4 weeks, permanently discontinue study drug.

Non-hematologic Toxicity	
Toxicity	Dose Modifications for Entinostat
Grade 3	Administer symptomatic remedies/ start prophylaxis. Hold dose until recovery to Grade 1 or baseline under the following directions: 
 1) If recovered within 1 week, resume study drug at prior dose. If not recovered within 1 week, continue to hold dose. 2) If recovered within 2-4 weeks, resume study drug as follows: 
 • If receiving 5 mg, restart study drug at 3 mg, • If receiving 3 mg, restart study drug at 2 mg, • If receiving 2 mg, permanently discontinue study drug. 3) If not recovered within 4 weeks, permanently discontinue study drug.
Recurrence of the same \geq Grade 3 toxicity, despite dose reduction	If the same \geq Grade 3 event recurs : 
 1) Administer symptomatic remedies/ start prophylaxis. Hold¹ dose until recovery to Grade 1 or baseline. 2) If recovered within 2 weeks, resume study drug as follows: 
 a. If receiving 5 mg, restart study drug at 3 mg, b. If receiving 3 mg, restart study drug at 2 mg, c. If receiving 2 mg, permanently discontinue study drug. 3) If the same \geq Grade 3 event recurs (i.e., third occurrence) despite entinostat dose reduction to 2 mg, as described above, discontinue study drug.
\leq Grade 2	Administer symptomatic remedies/start prophylaxis. Dosing of study drug may be interrupted at the Investigator's discretion. 
 • If dose is held for 4 consecutive weeks, permanently discontinue study drug¹. • If toxicity resolves, resume entinostat at the original dose.

If greater than 50% of doses are missed during any 6-week period, discontinue from study drug treatment. Entinostat must also be discontinued in case of permanent discontinuation of pembrolizumab.

Hematologic Toxicity	
Toxicity	Dose Modifications for Entinostat
\geq Grade 3 neutropenia, \geq Grade 3 uncomplicated thrombocytopenia, or Grade 2 complicated thrombocytopenia	Administer symptomatic remedies/start prophylaxis. Hold dose ¹ until recovery to Grade 1 or study baseline under the following direction: 
 1) If not recovered by next scheduled dose, skip the dose. If recovered by next scheduled dose, resume study drug at prior dose. 2) If receiving 2 mg dose, and not recovered by either of the next two scheduled doses, permanently discontinue study treatment. Otherwise, skip each dose. If recovered for either of these doses, resume study drug as follows: 
 a. If receiving 5 mg, restart study drug at 3 mg, b. If receiving 3 mg, restart study drug at 2 mg. 3) If not recovered within 4 weeks, permanently discontinue study drug.
Recurrence of the same hematologic toxicity	If the same hematologic toxicity recurs: 
 1) Administer symptomatic remedies/start prophylaxis. Hold¹ dose until recovery to Grade 1 or baseline. 2) If recovered within 2 weeks, resume study drug as follows: 
 • If receiving 5 mg, restart study drug at 3 mg, • If receiving 3 mg, restart study drug at 2 mg, • If receiving 2 mg, permanently discontinue study drug. 3) If the same \geq Grade 3 event recurs (i.e., third occurrence), despite entinostat dose reduction to 2 mg as described above, permanently discontinue study drug.

If greater than 50% of doses are missed during any 6-week period, discontinue from study drug treatment.

5.3.2 Dose Modification and toxicity management for immune-related AEs associated with pembrolizumab and combination therapy

AE (both non-serious and serious) associated with pembrolizumab exposure, including coadministration with additional compounds, may represent an immunologic etiology. These immune-related AEs (irAEs) may occur shortly after the first dose or several months after the last dose of pembrolizumab/combination treatment and may affect more than one body system simultaneously. Therefore, early recognition and initiation of treatment is critical to reduce complications. Based on existing clinical study data, most irAEs were reversible and could be managed with interruptions of pembrolizumab/combination treatment, administration of corticosteroids and/or other supportive care. For suspected irAEs, ensure adequate evaluation to confirm etiology or exclude other causes. Additional procedures or tests such as bronchoscopy, endoscopy, skin biopsy may be included as part of the evaluation. Dose modification and toxicity management guidelines for irAEs associated with pembrolizumab/combination treatment are provided in the table below. Pembrolizumab must be withheld for drug-related toxicities and severe or life-threatening AEs as per the table provided below. See Section 5.6 for supportive care guidelines, including use of corticosteroids and additional guidance on management of immune-mediated events (i.e., pneumonitis, diarrhea/colitis, Type 1 diabetes mellitus, hypophysitis, hyper/hypothyroidism, hepatotoxicity, renal insufficiency/nephritis, Steven's-Johnson Syndrome, and myocarditis).

Dosing interruptions are permitted in the case of medical/surgical events or logistical reasons not related to study therapy (e.g., elective surgery, radiation therapy, unrelated medical events, patient vacation, and/or holidays). Subjects should be placed back on study therapy within 3 weeks (i.e., 21 days) of the scheduled interruption, unless otherwise discussed with the Sponsor. The reason for interruption should be documented in the patient's study record. If pembrolizumab is permanently discontinued, entinostat must be discontinued as well.

Attribution of Toxicity:

When study interventions are administered in combination, attribution of an adverse event to a single component is likely to be difficult. Therefore, while the investigator may attribute a toxicity event to the combination, to entinostat alone or to pembrolizumab alone], for adverse events listed in the table below, both interventions must be held according to the criteria in the table below: Dose Modification and Toxicity Management Guidelines for Immune-Related Adverse Events Associated with Pembrolizumab and IO Combinations.

Holding Study Interventions:

When study interventions are administered in combination, if the AE is considered immune-related, both interventions should be held according to recommended dose modifications.

Restarting Study Interventions:

Participants may not have any dose modifications (no change in dose or schedule) of pembrolizumab in this study, as described in the table below.

- If the toxicity does not resolve or the criteria for resuming treatment are not met, the participant must be discontinued from all study interventions.
- If the toxicities do resolve and conditions are aligned with what is defined in the table below, the combination of entinostat and pembrolizumab may be restarted at the discretion of the investigator. In these cases where the toxicity is attributed to the combination or to entinostat alone, re-initiation of pembrolizumab as a monotherapy may be considered at the principal investigator's discretion.

Dose modification and toxicity management guidelines for immune-related AEs associated with pembrolizumab monotherapy and IO Combinations

General instructions:

1. Severe and life-threatening irAEs should be treated with IV corticosteroids followed by oral steroids. Other immunosuppressive treatment should begin if the irAEs are not controlled by corticosteroids.
2. Study intervention must be permanently discontinued if the irAE does not resolve or the corticosteroid dose is not ≤ 10 mg/day within 12 weeks of the last study intervention treatment.
3. The corticosteroid taper should begin when the irAE is \leq Grade 1 and continue at least 4 weeks.
4. If study intervention has been withheld, study intervention may resume after the irAE decreased to \leq Grade 1 after corticosteroid taper.

irAEs	Toxicity Grade (CTCAE v5.0)	Action With Pembrolizumab	Corticosteroid and/or Other Therapies	Monitoring and Follow-up
Pneumonitis	Grade 2	Withhold	
 • Administer corticosteroids (initial dose of 1 to 2 mg/kg prednisone or equivalent) followed by taper • Add prophylactic antibiotics for opportunistic infections 	
 • Monitor participants for signs and symptoms of pneumonitis • Evaluate participants with suspected pneumonitis with radiographic imaging and initiate corticosteroid treatment
	Recurrent Grade 2, Grade 3 or 4	Permanently discontinue		

irAEs	Toxicity Grade (CTCAE v5.0)	Action With Pembrolizumab	Corticosteroid and/or Other Therapies	Monitoring and Follow-up
Diarrhea/Colitis	Grade 2 or 3	Withhold	
 Administer corticosteroids (initial dose of 1 to 2 mg/kg prednisone or equivalent) followed by taper 	
 Monitor participants for signs and symptoms of enterocolitis (ie, diarrhea, abdominal pain, blood or mucus in stool with or without fever) and of bowel perforation (ie, peritoneal signs and ileus) Participants with \geqGrade 2 diarrhea suspecting colitis should consider GI consultation and performing endoscopy to rule out colitis Participants with diarrhea/colitis should be advised to drink liberal quantities of clear fluids. If sufficient oral fluid intake is not feasible, fluid and electrolytes should be substituted via IV infusion
	Recurrent Grade 3 or Grade 4	Permanently discontinue		
AST or ALT Elevation or Increased Bilirubin	Grade 2 ^a	Withhold	
 Administer corticosteroids (initial dose of 0.5 to 1 mg/kg prednisone or equivalent) followed by taper 	
 Monitor with liver function tests (consider weekly or more frequently until liver enzyme value returned to baseline or is stable)

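### Section 5.3.1, non-hematologic table: a repeat Grade 3 event at 5 mg that recovers within 1 week has two written restart doses (5 mg and 3 mg), and the restart dose after a Grade 2 or lower hold is undefined for a patient already reduced

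*Combined protocol and SAP*

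**What the plan says.** Section 5.3.1 of the protocol sets the entinostat dose after a toxicity in two tables. The starting dose is 5 mg weekly (Section 5.2), and the reduction steps are 5 mg to 3 mg to 2 mg, then discontinuation.

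Non-hematologic table:
- **Grade 3 row:** "If recovered within 1 week, resume study drug at prior dose". Recovery in 2 to 4 weeks brings a step down, and failure to recover within 4 weeks ends treatment. Nothing limits the row to a first event.
- **Recurrence row:** the heading restricts it to recurrence of the same event of at least "Grade 3 toxicity, despite dose reduction". The body opens with any recurrence of the same event, continues "If recovered within 2 weeks, resume study drug as follows", and gives as its first branch "If receiving 5 mg, restart study drug at 3 mg".
- **Grade 2 or lower row**, after a hold at the investigator's discretion: "If toxicity resolves, resume entinostat at the original dose". The term is not defined.

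Hematologic table:
- **First row:** "If recovered by next scheduled dose, resume study drug at prior dose". Its thrombocytopenia trigger is Grade 3 or higher "uncomplicated thrombocytopenia, or Grade 2 complicated thrombocytopenia".
- **Second row:** headed "Recurrence of the same hematologic toxicity", with no condition about an earlier reduction.

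**The concern.** A dose-modification table should give one answer for one event history. Here the non-hematologic recurrence row has a heading that excludes patients who were never reduced and a first branch that addresses exactly those patients. The Grade 3 row does not stop applying when the event repeats. The section also uses two terms for the restart dose, *prior* and *original*, and defines neither.

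What is at stake is first the safety of a patient with a repeated severe toxicity, whose next dose depends on which row is read. It is also adherence: Section 10.5 asks that the study be run as the protocol describes, and a restart cannot be classed as compliant or deviant when two rows give different doses. Finally, toxicity of the combination is a secondary objective (Section 2.2.3), and it would be described in a small group whose restart doses may not follow one rule.

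**Working it through.** The plan states no figure on this point, so the check is to apply the rows to the same patient and compare the results.

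**Step 1: can a patient have a repeat event while still on 5 mg?** Yes, and the table itself creates that patient. A first Grade 3 event at 5 mg that recovers within 1 week is resumed at 5 mg under the Grade 3 row. No reduction has taken place.

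**Step 2: the same Grade 3 event recurs in that patient.**

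| Recovery of the repeat event | Grade 3 row | Body of recurrence row | Result |
|---|---|---|---|
| Within 1 week | 5 mg | 3 mg | Rows differ |
| At 2 weeks | 3 mg | 3 mg | Rows agree |
| After 2 and up to 4 weeks | 3 mg | No rule | Recurrence row silent |
| Beyond 4 weeks | Discontinue | No rule | Recurrence row silent |

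The direct clash is confined to recovery within 1 week. The two restart doses differ by a factor of 5/3 = 1.67. Between 1 and 2 weeks the Grade 3 row literally says only to keep holding. With weekly dosing this adds little, and I do not press it.

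**Step 3: does the recurrence row settle which applies?** By its heading, a never-reduced patient is outside the row and falls back to the Grade 3 row (5 mg). By its 5 mg branch, the same patient is inside the row (3 mg). Heading and body point in opposite directions. For a patient on 3 mg or 2 mg the two rows also differ after recovery within 1 week (3 mg against 2 mg; 2 mg against discontinuation). That patient has been reduced, however, so the recurrence heading applies on its face.

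**Step 4: does the surrounding text settle it?** The opening sentence of Section 5.3.1, on the event that needs the greatest modification, ranks between different adverse events, not between two rows for the same event. The next sentence lets investigators be more conservative; it is a permission and names no governing row. Section 5.3.3 sends Grade 3 or higher events attributed to both drugs back to Sections 5.3.1 and 5.3.2, so it supplies no separate entinostat rule.

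**Step 5: the Grade 2 or lower row.** For a patient still on 5 mg, *original* and *prior* give the same dose. For a patient already on 3 mg or 2 mg they may not:

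| Dose before the hold | If *original* means the starting dose | If *original* means the dose before the hold |
|---|---|---|
| 3 mg | 5 mg (5/3 = 1.67-fold) | 3 mg |
| 2 mg | 5 mg (5/2 = 2.5-fold) | 2 mg |

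No passage says whether a reduction is permanent, so the text does not decide between the columns.

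**Step 6: the hematologic table.** The recurrence heading carries no condition about an earlier reduction, so a repeat event goes plainly to the reduction row. The table has no *original dose* rule. Neither restart problem is present there. What remains is the trigger: it names Grade 3 or higher uncomplicated and Grade 2 complicated thrombocytopenia. Read word for word, Grade 3-4 complicated thrombocytopenia is in neither entry.

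**The case against.** The best defense is that a sensible clinician would not be misled. The body of the recurrence row is the more specific rule for a repeated event, the investigator may always be more cautious, and the principal investigator oversees every patient's treatment (Section 10.8), so different practice between sites is speculative. Much of this stands, and I make no claim about variation between sites. It does not remove the clash: the more specific row excludes the never-reduced patient by its own heading, and permission to be cautious does not say what the rule is.

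Some stronger readings are tempting, and the documents do not support them:
- A reader might infer that the Grade 2 or lower row orders a reduced patient back to 5 mg. The wording allows that reading but does not compel it; the dose before the hold is also a fair meaning. This is an undefined term, not a proven instruction to re-escalate.
- A reader might infer that the hematologic table has the same restart conflict. Step 6 shows that it does not.
- A reader might infer that Grade 3-4 complicated thrombocytopenia has no action. If the entries are thresholds, with a lower one when the event is complicated, it exceeds both and is covered. If the source file carries a greater-than-or-equal sign before Grade 2, this lesser point falls away.
- A reader might try to count affected patients from the background safety figures in Section 1.4.6.2.2. Those are serious-event and any-grade rates, not rates of dose reduction or of later holds, and the enrollment target of 14 in Section 9.2 allows for screen failures. No count or probability can be supported.

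**Conclusion.** The non-hematologic table is wrong as written. For one defined history (a repeat of the same Grade 3 event, in a patient still on 5 mg, recovering within 1 week) it gives both 5 mg and 3 mg. This rests only on the text of the rows and on the Grade 3 row not being limited to first events. The silence of the recurrence row after 2 weeks is a gap in the same row.

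The undefined *original dose* is a real ambiguity that matters only for patients already at 3 mg or 2 mg. The complicated-thrombocytopenia wording is a minor clarification.

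A reader might infer harm to the primary analysis. There is none to claim: conversion is read on the day 22 biopsy after three weeks of entinostat, and the sample size and error rates in Section 9.2 do not use these rules. Nor does the visible text plan a dose-intensity analysis that would be affected. The case for a change rests on patient safety and on having one rule to follow. I take no view on which restart dose is clinically right.

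**What to change.** Reconcile the rows of Section 5.3.1 so that each event history leads to one restart dose:

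1. Make the non-hematologic recurrence heading, its 5 mg branch and the Grade 3 row agree. Say whether the Grade 3 row applies only to a first event, and which row governs a repeat event that takes more than 2 weeks to recover.
2. Use one defined term for the restart dose in every row, and state how it applies to a patient whose dose has already been reduced.
3. State which row covers Grade 3-4 complicated thrombocytopenia.

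The sponsor and the drug supplier choose the clinical rule in each case. The cost is wording in one section at the next amendment, with no added visits, tests or patients.
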